8.1 Definition of an Adverse Event

An AE is any untoward medical occurrence associated with the use of a drug in humans, whether or not considered drug-related.

An AE can therefore be:

- Any unfavorable and unintended medical diagnosis, sign, or symptom
- Any new undesirable medical occurrence or unfavorable or unintended change in a pre-existing condition that occurs during or after study treatment
- Vital sign or ophthalmic assessment that is assessed as clinically significant and different from baseline (eg, requiring discontinuation of study treatment, specific treatment, or a change in subject management); if possible, changes in laboratory results or changes in vital signs that meet the definition of an AE should be reported as a medical diagnosis rather than as the abnormal value (eg, "hypertension" rather than "blood pressure increased")

The following are special considerations when determining and reporting AEs:

- Whenever possible, the investigator should group signs or symptoms that constitute a single diagnosis under a single AE term (eg, “cough, rhinitis, and sneezing” might be grouped together as “upper respiratory tract infection”).
- Progression of neovascular AMD, including worsening of anticipated clinical signs or symptoms, which are collected as clinical efficacy variable and assessed as unequivocally associated with the disease progression and/or lack of efficacy, should NOT be reported as AEs unless disease progression is greater than anticipated in the natural course of the disease.
- A pre-existing condition is not considered an AE unless the condition worsens (increases in frequency, severity, or specificity) during or following study drug administration. Fluctuations in a pre-existing condition should be assessed by the investigator, and those that fall within the limits of expected fluctuations for the disease state (and are not assessed as worsening of the disease) should not be considered AEs. Any change assessed as clinically significant worsening of the disease from baseline must be documented as an AE.
- Elective surgery or routine diagnostic procedures are not considered AEs. However, an untoward medical event occurring during the prescheduled elective surgery or diagnostic procedure should be recorded as an AE.
- Death itself is not considered an AE; it is instead the outcome of an AE.

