A treatment emergent adverse event (TEAE) is an AE with an onset anytime from when the subject has received study drug through 30 days after the study ends whether or not it is considered causally related to the study drug.

Note: AEs must be collected once informed consent has been obtained, regardless of whether or not the subject has been administered study drug.

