### 8.2 Missing or Inconclusive Data Handling

In general, there will be no imputation of missing data other than for partial or missing dates where complete dates are required to flag data as treatment-emergent or concomitant with treatment. Partial/missing start and end dates for AEs and concomitant medications will be imputed as follows:

Partial/missing start date:

- Dates with missing day only will be imputed as the 1st of the month unless the month and year are same as the month and year of first dose of study medication, in which case missing day will be imputed as the first dose day of study medication.

- Dates with both day and month missing will be imputed as 1 Jan unless the year is same as the year of first dose of study medication, in which case missing day and month will be imputed as the first dose day and month of study medication.
- Completely missing dates will not be imputed.

Partial/missing end date:

- Dates with missing day only will be imputed as the last day of the month unless the month and year are the same as the month and year of the last dose of study medication, in which case missing day will be imputed as the last dose day of study medication.
- Dates with both day and month missing will be imputed as 31 Dec unless the year is same as the year of the last dose of study medication, in which case missing day and month will be imputed as the last dose day and month of study medication.
- If the ongoing flag is missing or “Yes” then the date will not be imputed unless death date is available, in which case the missing date will be imputed as the death date. If ongoing is “No” then the missing end date will be imputed as the last dose date.

The original dates will be displayed in data listings and the imputed dates will be used in derivations only (study day, treatment-emergence status, etc).

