#### 13.1 Adverse Events

An adverse event (AE) is defined as any untoward medical occurrence associated with the use of a drug in humans, whether it is considered drug related. An AE can therefore be any unfavorable and unintended medical diagnosis, sign, or symptom; any new undesirable medical occurrence or unfavorable or unintended change in a pre-existing condition that occurs during or after study treatment; or laboratory abnormality, vital sign, or ophthalmic assessment that is assessed as clinically significant and different from baseline (e.g., requiring discontinuation of study treatment, specific treatment, or a change in subject management). If possible, changes in laboratory results or changes in vital signs that meet the definition of an AE should be reported as a medical diagnosis rather than as the abnormal value. All AEs will be coded using MedDRA Version 22.0.

A treatment-emergent adverse event (TEAE) is an AE with an onset anytime from when the subject has received study drug through 30 days after the study ends whether it is considered causally related to the study drug. Adverse events recorded in the eCRF which began prior to treatment will not be included in the summary tables but will be included in the AE data listings. An SAE is any event that involves or results in any of the following outcomes:

- Death
- Life-threatening occurrence (i.e., if in the view of the investigator or Sponsor, the event's occurrence placed the subject at risk of death at the time of the event; it does not refer to an event which hypothetically might have caused death if it were more severe)
- Requires in-patient hospitalization or prolongation of existing hospitalization (hospitalization for elective surgery for a pre-existing condition or for surgery planned before study entry is not considered an SAE)
- A persistent or significant disability/incapacity (permanent or substantial disruption of the subject's ability to perform normal life functions); this definition is not intended to include experiences of relatively minor or temporary medical significance
- Congenital anomaly/birth defect (an AE that occurs in the child or fetus of a subject exposed to study drug prior to conception or during pregnancy)

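### The treatment-emergent rule uses onset date alone: it leaves open how a screening AE that worsens after injection is counted, and its start-date imputation ignores a recorded end date

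*SAP*

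**What the plan says.** Protocol 8.1 sets the rule: "A treatment emergent adverse event (TEAE) is an AE with an onset anytime from when the subject has received study drug", with the period running to 30 days past study end. SAP 13.1 repeats it: "A treatment-emergent adverse event (TEAE) is an AE with an onset anytime from when the subject has received study drug through 30 days". Neither mentions worsening.

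SAP 13.1 then states: "Adverse events recorded in the eCRF which began prior to treatment will not be included in the summary tables". The sentence goes on to keep these events in the AE listings, and SAP section 16 plans Listing 16.2.7.1 for all adverse events.

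Both documents treat worsening as an AE in some circumstances. The AE definition in SAP 13.1 covers an "unfavorable or unintended change in a pre-existing condition that occurs during or after study treatment". Protocol 8.1 says: "A pre-existing condition is not considered an AE unless the condition worsens (increases in frequency, severity, or specificity) during or following study drug administration", and also: "Any change assessed as clinically significant worsening of the disease from baseline must be documented as an AE".

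On dates, SAP 8.2 imputes partial start dates so that events can be flagged as treatment-emergent. If the recorded month and year, or the year alone, match those of dosing, the missing parts take the dosing date. It then says: "Completely missing dates will not be imputed".

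The primary endpoint is the occurrence of ocular and non-ocular AEs and SAEs (Protocol 9.2.1, SAP section 3). The AE incidence tables described in SAP 13.1 and listed in SAP section 15 are TEAE tables.

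**The concern.** AEs are collected from consent and asked about at screening and at baseline, so AE records with a pre-dose onset are an expected input. Suppose an eye event is on the AE form before Day 1 and becomes worse after the injection. That worsening is what a safety study of an intravitreal depot should count. Under an onset-only rule, whether it is counted depends on how the site enters it.

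The date rules add two smaller problems. One can turn an event that was over before dosing into a TEAE. The other leaves an undated event with no classification. The first problem and the third can hide events that may be related to GB-102; the second adds events that cannot be. With 10 subjects per dose, one misclassified subject visibly changes a reported incidence.

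**Working it through.** **1. A screening AE that worsens after dosing.** There are three ways it can reach the database:

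- The condition is only in the medical history and worsens after dosing. Protocol 8.1 makes the worsening an AE. Its onset is after dosing, so it is a TEAE and is tabulated.
- The condition is already an AE record, and the site opens a second record dated at the worsening. This is a TEAE and is tabulated.
- The condition is already an AE record, and the site raises the severity on that record. The onset stays before dosing, the TEAE definition is not met, and SAP 13.1 keeps the event out of the summary tables.

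The second and third routes are both compatible with the text. Protocol section 8 asks for onset date and severity for each AE but does not say when a change of severity starts a new record. The sentence on pre-existing conditions concerns something that is not yet an AE. The duty to document worsening as an AE can be read as met when the AE is already on file. The nearest rule is Protocol 8.8, which asks for a follow-up report when an ongoing SAE worsens and is silent on onset.

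**2. Partial start date with a known end date.** Let D be the dosing date and E the recorded end date, with E before D. The start day is missing and the recorded month and year are those of D (or day and month are missing and the year is that of D). SAP 8.2 sets the start S = D. Then S is later than E, so the event starts after it ended, and it is flagged as a TEAE although it was over before dosing.

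**3. Completely missing start date.** SAP 8.2 imputes nothing and states no default. The event cannot be shown to meet the TEAE definition, nor to have begun before treatment. Its status is undefined.

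**4. Scale.** Inputs: 10 subjects per dose and 20 in total (SAP 4.1); detectable AE rates of 15% overall and 30% per dose at about 95% confidence (SAP section 5, Protocol 9.4).

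- The plan's figures reproduce by the rule of three: 3/20 = 15% and 3/10 = 30%. Exactly, the chance of at least one event is 1 − (1 − 0.15)^20 = 96.1% and 1 − (1 − 0.30)^10 = 97.2%.
- One subject is 1/10 = 10 points of a dose group and 1/20 = 5 points overall.
- One-sided 95% upper bound with no events: 1 − 0.05^(1/n), which is 25.9% for n = 10 and 13.9% for n = 20. With one event, the bound solves (1 − p)^n + n p (1 − p)^(n−1) = 0.05, which gives 39.4% and 21.6%. Losing one subject's event from the table therefore lowers the bound from 39.4% to 25.9% in a dose group, and from 21.6% to 13.9% overall.
- Assumption, since the documents give no such share: a fraction q of subjects with an event is missed. The chance of seeing at least one is then 1 − (1 − p(1 − q))^n:

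| q | n = 20, p = 15% | n = 10, p = 30% |
|---|---|---|
| 0 | 96.1% | 97.2% |
| 10% | 94.5% | 95.7% |
| 20% | 92.2% | 93.6% |
| 30% | 89.1% | 90.5% |

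**The case against.** A reader might infer that a screening event which worsens, or an event without an onset date, disappears from every table of the primary endpoint. The documents do not support that, for four reasons:

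- Worsening of a pre-existing condition is itself an AE in both documents. Entered with its own date, it is tabulated. Loss requires the site to keep the old record and its onset, which no text instructs. The eCRF completion guidelines named in Protocol section 11 are not among the documents and may settle the matter.
- Excluded events remain in the all-AE listing, which can be read subject by subject in a 20-subject open-label study.
- Ocular worsening can also show in the BCVA, slit-lamp, ophthalmoscopy and IOP summaries (SAP 13.2 to 13.5), which do not depend on AE onset.
- A wholly missing start date should be rare. Onset is a required item, missing data are queried, and an event known only to fall in the dosing year is given the dosing date. SAP 8.2 does not say that undated events are excluded.

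It can also be said that the end-date problem over-counts TEAEs and so errs on the cautious side, and that no frequency is given for any of these cases.

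All of this stands, and it limits the point to events that can be left out rather than events that are lost. It does not remove the point. A listing gives no incidence, and the examination tables do not report AE occurrence. Protocol section 11 allows an item to be marked unknown, so an undated event can survive to database lock. A false TEAE does not compensate for a missed true one. There is also a weakness in the listings: SAP 13.1 promises a listing of all serious AEs, but section 16 titles it as treatment-emergent. A screening AE that becomes serious under its old record might therefore miss that listing too.

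**Conclusion.** The concern holds in limited form. The onset-only rule does not settle how a screening AE that worsens after injection is counted, and one permissible way of recording it keeps it out of the TEAE incidence tables. SAP 8.2, applied literally, also makes a false TEAE of some events that ended before dosing, and it leaves an AE with no start date unclassified.

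The number affected is probably small: the pre-dose window is at most 30 days and 20 subjects are planned. The size is 10 points of a dose group and 5 points overall per subject, if that subject has no other event counted in the same table row. The direction is mixed, since the worsening gap and the undated case can lower the incidence while the end-date gap raises it.

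The documents do not support reading this as a threat to the sample size. They say the size was not chosen for hypothesis testing, none is planned, and the 15% and 30% figures reproduce. The shares of missed events in the table above are assumptions that show a range, not estimates.

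This is a modest defect in the rules for the primary endpoint. It should be settled before database lock.

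**What to change.** - **Protocol 8.1 and SAP 13.1:** define a TEAE as an AE with onset after dosing, or a pre-dose AE that increases in severity or becomes serious after dosing. Such an event is recorded, or counted, with onset at the date of worsening. Add a matching line to the eCRF completion guidelines so that sites enter it the same way.
- **SAP 8.2, completely missing start date:** count the AE as treatment-emergent unless its recorded end date is before dosing. The end date must be a recorded one, because SAP 8.2 can impute a missing end date as the last dose date, which is Day 1 in this single-injection study.
- **SAP 8.2, partial start date:** do not let an imputed start fall after a recorded end.

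The cost is a few sentences in the two documents and one guideline line. Reported TEAE incidence may rise slightly. No assessment, visit or sample size changes.

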### 13.2 BCVA (ETDRS)

The observed and change from baseline BCVA letter score will be summarized for the study eye and non-study eye using continuous descriptive statistics by visit for each cohort and for all subjects combined. A subject listing of visual acuity will also be produced. This listing will include a variable that indicates if a subject had a visual acuity worsening from baseline of  $\geq 10$  letters.

### 13.3 Slit-Lamp Biomicroscopy Examination

A slit-lamp biomicroscopy examination of the eyelid, cornea, conjunctiva, anterior chamber, iris, pupil, lens, lens status, and Age-Related Eye Disease Study (AREDS) scores for Nuclear, Cortical, and PCS opacity will be performed at each visit. The results will be graded as normal, abnormal not clinically significant (NCS), or abnormal clinically significant (CS) for all but the lens status and AREDS scores. Lens status will be denoted phakic, pseudophakic, or aphakic. AREDS opacity scores are <1, 1, 1.5, 2, 2.5, 3, or >3. Anterior chamber cells and flare will also be assessed using categorical responses that range from 0 to 4+, as described below.

#### Anterior Chamber Cells:

| Grade | Number of cells |
|-------|-----------------|
| 0     | None            |
| +0.5  | 1 – 5           |
| +1    | 6 - 15          |
| +2    | 16 – 25         |
| +3    | 26 – 50         |
| +4    | > 50            |

#### Anterior Chamber Flare:

| Grade | Description                           |
|-------|---------------------------------------|
| 0     | None                                  |
| +1    | Trace                                 |
| +2    | Moderate (iris and lens detail clear) |

- +3 Marked (iris and lens detail hazy)
- +4 Intense (fibrin or plastic aqueous)

The results will be summarized using counts and percentages for each cohort and for all GB-102 treated subjects combined at each visit for each eye (study eye and non-study eye). Percentages will be based on the number of subjects in each cohort with responses. Shift tables for each biomicroscopy parameter will also be provided comparing each follow-up visit to baseline. A subject listing of the slit-lamp biomicroscopy parameters will also be produced.

### **13.4 Dilated Ophthalmoscopy**

A dilated fundus examination of the vitreous, macula, peripheral retina, choroid, and optic nerve will be performed at each visit. The results will be graded as normal, abnormal NCS, or abnormal CS. The results will be summarized using counts and percentages for each cohort and for all subjects at each visit for each eye (study eye and non-study eye). Percentages will be based on the number of subjects in each cohort with responses. A shift table for the dilated ophthalmoscopy parameters will also be provided comparing each follow-up visit to baseline. A subject listing of the dilated ophthalmoscopy parameters will also be produced.

### **13.5 Intraocular Pressure (IOP)**

Intraocular pressure (IOP) will be assessed using Goldmann applanation tonometry or Tono-Pen at each visit. Results will be taken from a single measurement and will be recorded in mmHg. Clinically relevant change in IOP indicates increase from baseline is at least 10 mmHg and absolute value is at least 25 mmHg at a visit. The IOP values, changes from baseline, and clinically relevant change for each eye (study eye and non-study eye) will be summarized using continuous descriptive statistics by visit and eye for each cohort and for all subjects combined. A subject listing of IOP will also be produced.

### **13.6 Physical Examination**

The physical examination will consist of, at a minimum, a routine evaluation of the organ systems including general appearance, neck, head, ears, nose, throat, cardiovascular, respiratory, abdomen, and skin/extremities. At the final study visit, the physical examination will include a query of the subject to determine if changes in his/her physical condition have occurred since the screening examination. A subject listing of the physical examination results will be produced.

### **13.7 Vital Signs**

Vital signs, including height, heart rate (HR) and systolic and diastolic blood pressure will be measured at Screening, Day 1, and Month 6. Body weight will be measured at Screening and Month 6. Height will be measured only at Screening. Changes from baseline will be summarized at Month 6 for applicable parameters. A subject listing of the vital signs results will also be produced.

**13.8 Blood Chemistry**

Blood samples for Hemoglobin A1c (nonfasting) will be collected prior to administration of study drug. Screening laboratory tests may be repeated once at the discretion of the Investigator. A subject listing of the blood chemistry results will be produced.

**13.9 Pregnancy Testing**

Urine pregnancy test will be conducted on women of childbearing potential as appropriate. Women of childbearing potential (i.e., not postmenopausal for at least 12 months or not surgically sterile [bilateral tubal ligation, hysterectomy, or bilateral oophorectomy]) must have a negative urine pregnancy test at Screening and must use adequate birth control throughout the study if she has a nonsurgically sterile male sexual partner. A subject listing of urine pregnancy test results will be produced.

**14. Interim Analyses**

Once all subjects complete the 3-month visit, an interim analysis (IA) will be performed on safety data. No statistical adjustments will be made for this exploratory study and due to the analysis being limited to safety endpoints and due to the absence of any hypothesis testing.

## 15. Tables

Tables that will be included in the topline delivery are shown in boldface italics font.

| Table Number          | Title  | POPULATION   |
|-----------------------|--|--|
| Table 14.1.1.1 | Subject Disposition  | All Enrolled Subjects  |
| Table 14.1.1.2        | Subject Enrollment Status  | All Subjects Including Screen Failures                                       |
| Table 14.1.2.1 | Demographic and Pretreatment Variables in Study Eye  | Full Analysis Set  |
| Table 14.1.2.2        | Demographic and Pretreatment Variables in Study Eye  | Safety Analysis Set  |
| Table 14.1.2.3        | Demographic and Pretreatment Variables in Study Eye  | Per Protocol Analysis Set  |
| Table 14.1.4.1        | Ocular Medical History   | Safety Analysis Set  |
| Table 14.1.4.2        | Non-Ocular Medical History   | Safety Analysis Set  |
| Table 14.1.5.1        | Ocular Prior Medications   | Safety Analysis Set  |
| Table 14.1.5.2        | Ocular Concomitant Medications   | Safety Analysis Set  |
| Table 14.1.5.3        | Non-Ocular Prior Medications   | Safety Analysis Set  |
| Table 14.1.5.4        | Non-Ocular Concomitant Medications   | Safety Analysis Set  |
| Table 14.1.6          | Study Drug Administration  | Safety Analysis Set  |
| Table 14.2.1.1 | Change from Baseline in Number of Letters Read Correctly (using BCVA) in the Study Eye at Scheduled Visits | Full Analysis Set – As Observed (Including Rescue Treatment)   |
| Table 14.2.1.2        | Change from Baseline in Number of Letters Read Correctly (using BCVA) in the Study Eye at Scheduled Visits               | Per Protocol Analysis Set – As Observed (Including Rescue Treatment)         |
| Table 14.2.1.3        | Change from Baseline in Number of Letters Read Correctly (using BCVA) in the Study Eye at Scheduled Visits by Diagnosis  | Full Analysis Set – As Observed (Including Rescue Treatment)                 |
| Table 14.2.1.4        | Change from Baseline in Number of Letters Read Correctly (using BCVA) in the Study Eye at Scheduled Visits by Diagnosis  | Per Protocol Analysis Set – As Observed (Including Rescue Treatment)         |
| Table 14.2.1.5 | Change from Baseline in Number of Letters Read Correctly (using BCVA) in the Study Eye at Scheduled Visits | Full Analysis Set – LOCF With Censoring For Rescue |

|                       |  |   |
|-----------------------|--|---|
| Table 14.2.1.6        | Change from Baseline in Number of Letters Read Correctly (using BCVA) in the Study Eye at Scheduled Visits                 | Per Protocol Analysis Set – LOCF With Censoring For Rescue  |
| Table 14.2.1.7        | Change from Baseline in Number of Letters Read Correctly (using BCVA) in the Study Eye at Scheduled Visits by Diagnosis    | Full Analysis Set – LOCF With Censoring For Rescue          |
| Table 14.2.1.8        | Change from Baseline in Number of Letters Read Correctly (using BCVA) in the Study Eye at Scheduled Visits by Diagnosis    | Per Protocol Analysis Set – LOCF With Censoring For Rescue  |
| Table 14.2.2.1 | Change from Baseline in Retinal CST (Using SD-OCT in <math>\mu\text{m}</math>) in the Study Eye at Scheduled Visits | Full Analysis Set – As Observed (Including Rescue Treatment)     |
| Table 14.2.2.2        | Change from Baseline in Retinal CST (Using SD-OCT in $\mu\text{m}$ ) in the Study Eye at Scheduled Visits                  | Per Protocol Analysis Set – As Observed (Including Rescue Treatment)    |
| Table 14.2.2.3        | Change from Baseline in Retinal CST (Using SD-OCT in $\mu\text{m}$ ) in the Study Eye at Scheduled Visits by Diagnosis     | Full Analysis Set – As Observed (Including Rescue Treatment)            |
| Table 14.2.2.4        | Change from Baseline in Retinal CST (Using SD-OCT in $\mu\text{m}$ ) in the Study Eye at Scheduled Visits by Diagnosis     | Per Protocol Analysis Set – As Observed (Including Rescue Treatment)    |
| Table 14.2.2.5 | Change from Baseline in Retinal CST (Using SD-OCT in <math>\mu\text{m}</math>) in the Study Eye at Scheduled Visits | Full Analysis Set – LOCF With Censoring For Rescue   |
| Table 14.2.2.6        | Change from Baseline in Retinal CST (Using SD-OCT in $\mu\text{m}$ ) in the Study Eye at Scheduled Visits                  | Per Protocol Analysis Set – LOCF With Censoring For Rescue  |
| Table 14.2.2.7        | Change from Baseline in Retinal CST (Using SD-OCT in $\mu\text{m}$ ) in the Study Eye at Scheduled Visits by Diagnosis     | Full Analysis Set – LOCF With Censoring For Rescue          |
| Table 14.2.2.8        | Change from Baseline in Retinal CST (Using SD-OCT in $\mu\text{m}$ ) in the Study Eye at Scheduled Visits by Diagnosis     | Per Protocol Analysis Set – LOCF With Censoring For Rescue  |
| Table 14.2.3.1 | Time to Receipt of Rescue Treatment Using Kaplan-Meier Approach   | Full Analysis Set  |
| Table 14.2.3.2        | Time to Receipt of Rescue Treatment Using Kaplan-Meier Approach  | Per Protocol Analysis Set   |
| Table 14.2.3.3        | Time to Receipt of Rescue Treatment Using Kaplan-Meier Approach by Diagnosis   | Full Analysis Set   |
| Table 14.2.3.4        | Time to Receipt of Rescue Treatment Using Kaplan-Meier Approach by Diagnosis   | Per Protocol Analysis Set   |

|                       |  |                           |
|-----------------------|--|---------------------------|
| Table 14.2.3.5        | Mean Time to Receipt of First Rescue Treatment Among Rescued Subjects  | Full Analysis Set         |
| Table 14.2.3.6        | Mean Time to Receipt of First Rescue Treatment Among Rescued Subjects  | Per Protocol Analysis Set |
| Table 14.2.3.7        | Mean Time to Receipt of First Rescue Treatment Among Rescued Subjects by Diagnosis   | Full Analysis Set         |
| Table 14.2.3.8        | Mean Time to Receipt of First Rescue Treatment Among Rescued Subjects by Diagnosis   | Per Protocol Analysis Set |
| Table 14.2.4.1 | Proportion of Subjects Receiving Rescue Treatment by Visit  | Full Analysis Set  |
| Table 14.2.4.2        | Proportion of Subjects Receiving Rescue Treatment by Visit   | Per Protocol Analysis Set |
| Table 14.2.4.3        | Proportion of Subjects Receiving Rescue Treatment by Visit, and Diagnosis  | Full Analysis Set         |
| Table 14.2.4.4        | Proportion of Subjects Receiving Rescue Treatment by Visit, and Diagnosis  | Per Protocol Analysis Set |
| Table 14.2.4.5        | Contingency Table Showing Proportion of Subjects Receiving Rescue Treatment and Meeting Treatment Criteria by Visit                | Full Analysis Set         |
| Table 14.2.4.6        | Contingency Table Showing Proportion of Subjects Receiving Rescue Treatment and Meeting Treatment Criteria by Visit                | Per Protocol Analysis Set |
| Table 14.2.4.7        | Contingency Table Showing Proportion of Subjects Receiving Rescue Treatment and Meeting Treatment Criteria by Visit, and Diagnosis | Full Analysis Set         |
| Table 14.2.4.8        | Contingency Table Showing Proportion of Subjects Receiving Rescue Treatment and Meeting Treatment Criteria by Visit, and Diagnosis | Per Protocol Analysis Set |
| Table 14.2.5.1        | Total Number of Rescue Treatments Received by Each Subject   | Full Analysis Set         |
| Table 14.2.5.2        | Total Number of Rescue Treatments Received by Each Subject   | Per Protocol Analysis Set |
| Table 14.2.5.3        | Total Number of Rescue Treatments Received by Each Subject, and Diagnosis  | Full Analysis Set         |
| Table 14.2.5.4        | Total Number of Rescue Treatments Received by Each Subject, and Diagnosis  | Per Protocol Analysis Set |
| Table 14.2.6.1        | Time in the Study From First Rescue Treatment Received by Each Subject   | Full Analysis Set         |

|                       |  |   |
|-----------------------|--|---|
| Table 14.2.6.2        | Time in the Study From First Rescue Treatment Received by Each Subject   | Per Protocol Analysis Set                                       |
| Table 14.2.6.3        | Time in the Study From First Rescue Treatment Received by Each Subject, and Diagnosis  | Full Analysis Set   |
| Table 14.2.6.4        | Time in the Study From First Rescue Treatment Received by Each Subject, and Diagnosis  | Per Protocol Analysis Set                                       |
| Table 14.2.8.1        | Change in Number of Letters Read Correctly (Using BCVA) in Response to Anti-VEGF Rescue Treatment at Scheduled Visits in the Study Eye               | Full Analysis Set with a Rescue Treatment – As Observed         |
| Table 14.2.8.2        | Change in Number of Letters Read Correctly (Using BCVA) in Response to Anti-VEGF Rescue Treatment at Scheduled Visits in the Study Eye               | Per Protocol Analysis Set with a Rescue Treatment – As Observed |
| Table 14.2.8.3        | Change in Number of Letters Read Correctly (Using BCVA) in Response to Anti-VEGF Rescue Treatment at Scheduled Visits in the Study Eye, by Diagnosis | Full Analysis Set with a Rescue Treatment – As Observed         |
| Table 14.2.8.4        | Change in Number of Letters Read Correctly (Using BCVA) in Response to Anti-VEGF Rescue Treatment at Scheduled Visits in the Study Eye by Diagnosis  | Per Protocol Analysis Set with a Rescue Treatment – As Observed |
| Table 14.2.9.1        | Change in Retinal CST (Using SD-OCT in $\mu\text{m}$ ) in Response to Anti-VEGF Rescue Treatment at Scheduled Visits in the Study Eye                | Full Analysis Set with a Rescue Treatment – As Observed         |
| Table 14.2.9.2        | Change in Retinal CST (Using SD-OCT in $\mu\text{m}$ ) in Response to Anti-VEGF Rescue Treatment at Scheduled Visits in the Study Eye                | Per Protocol Analysis Set with a Rescue Treatment – As Observed |
| Table 14.2.9.3        | Change in Retinal CST (Using SD-OCT in $\mu\text{m}$ ) in Response to Anti-VEGF Rescue Treatment at Scheduled Visits in the Study Eye by Diagnosis   | Full Analysis Set with a Rescue Treatment – As Observed         |
| Table 14.2.9.4        | Change in Retinal CST (Using SD-OCT in $\mu\text{m}$ ) in Response to Anti-VEGF Rescue Treatment at Scheduled Visits in the Study Eye by Diagnosis   | Per Protocol Analysis Set with a Rescue Treatment – As Observed |
| Table 14.3.1.1 | Overall Summary of Adverse Event   | Safety Analysis Set                               |
| Table 14.3.2.1 | All Ocular Treatment-Emergent Adverse Events in the Study Eye  | Safety Analysis Set                               |
| Table 14.3.2.2        | All Ocular Treatment-Emergent Adverse Events in the Non-Study Eye  | Safety Analysis Set   |
| Table 14.3.2.3        | All Non-Ocular Treatment-Emergent Adverse Events   | Safety Analysis Set   |
| Table 14.3.3.1        | All Ocular Treatment-Emergent Adverse Events Suspected to be Related to Investigational Product in the Study Eye                                     | Safety Analysis Set   |

|                       |   |                            |
|-----------------------|---|----------------------------|
| Table 14.3.3.2        | All Ocular Treatment-Emergent Adverse Events Suspected to be Related to Investigational Product in the Non-Study Eye                  | Safety Analysis Set        |
| Table 14.3.3.3        | All Non-Ocular Treatment-Emergent Adverse Events Suspected to be Related to Investigational Product                                   | Safety Analysis Set        |
| Table 14.3.4.1 | All Ocular Treatment-Emergent Serious Adverse Events in the Study Eye  | Safety Analysis Set |
| Table 14.3.4.2        | All Ocular Treatment-Emergent Serious Adverse Events in the Non-Study Eye   | Safety Analysis Set        |
| Table 14.3.4.3 | All Non-Ocular Treatment-Emergent Serious Adverse Events   | Safety Analysis Set |
| Table 14.3.5.1        | All Serious Ocular Treatment-Emergent Adverse Events Suspected to be Related to Investigational Product in the Study Eye              | Safety Analysis Set        |
| Table 14.3.5.2        | All Serious Ocular Treatment-Emergent Adverse Events Suspected to be Related to Investigational Product in the Non-Study Eye          | Safety Analysis Set        |
| Table 14.3.5.3        | All Serious Non-Ocular Treatment-Emergent Adverse Events Suspected to be Related to Investigational Product                           | Safety Analysis Set        |
| Table 14.3.6.1        | Incidence of Ocular Treatment-Emergent Adverse Events in the Study Eye by Maximum Severity, System Organ Class and Preferred Term     | Safety Analysis Set        |
| Table 14.3.6.2        | Incidence of Ocular Treatment-Emergent Adverse Events in the Non-Study Eye by Maximum Severity, System Organ Class and Preferred Term | Safety Analysis Set        |
| Table 14.3.6.3        | Incidence of Non-Ocular Treatment-Emergent Adverse Events by Maximum Severity, System Organ Class and Preferred Term                  | Safety Analysis Set        |
| Table 14.3.7          | All Treatment-Emergent Adverse Events Leading to Premature Study Discontinuation  | Safety Analysis Set        |
| Table 14.3.8          | Best Corrected Visual Acuity (BCVA) In Letters (ETDRS)  | Safety Analysis Set        |
| Table 14.3.9.1        | Slit-Lamp Biomicroscopy   | Safety Analysis Set        |
| Table 14.3.9.2        | Shifts in Slit-Lamp Biomicroscopy from Baseline to Each Post-Baseline Visit: Normal/Abnormal Responses                                | Safety Analysis Set        |
| Table 14.3.9.3        | Shifts in Slit-Lamp Biomicroscopy from Baseline to Each Post-Baseline Visit: AREDS Scores and Anterior Chamber Cells and Flare        | Safety Analysis Set        |
| Table 14.3.10.1       | Dilated Ophthalmoscopy  | Safety Analysis Set        |

|                 |  |                     |
|-----------------|--|---------------------|
| Table 14.3.10.2 | Shifts in Dilated Ophthalmoscopy from Baseline to Each Post-Baseline Visit   | Safety Analysis Set |
| Table 14.3.11   | Intraocular Pressure   | Safety Analysis Set |
| Table 14.3.12   | Vital Signs  | Safety Analysis Set |
| Table 14.3.13.1 | All Ocular Treatment-Emergent Adverse Events in the Study Eye by Site  | Safety Analysis Set |
| Table 14.3.13.2 | All Ocular Treatment-Emergent Adverse Events in the Non-Study Eye by Site  | Safety Analysis Set |
| Table 14.3.13.3 | All Non-Ocular Treatment-Emergent Adverse Events by Site   | Safety Analysis Set |
| Table 14.3.14.1 | Incidence of Ocular Treatment-Emergent Adverse Events in the Study Eye by Maximum Severity, System Organ Class, Preferred Term, and Site     | Safety Analysis Set |
| Table 14.3.14.2 | Incidence of Ocular Treatment-Emergent Adverse Events in the Non-Study Eye by Maximum Severity, System Organ Class, Preferred Term, and Site | Safety Analysis Set |
| Table 14.3.14.3 | Incidence of Non-Ocular Treatment-Emergent Adverse Events by Maximum Severity, System Organ Class, Preferred Term, and Site                  | Safety Analysis Set |
| Table 14.3.15.1 | All Ocular Treatment-Emergent Adverse Events Suspected to be Related to Investigational Product in the Study Eye by Site                     | Safety Analysis Set |
| Table 14.3.15.2 | All Ocular Treatment-Emergent Adverse Events Suspected to be Related to Investigational Product in the Non-Study Eye by Site                 | Safety Analysis Set |
| Table 14.3.15.3 | All Non-Ocular Treatment-Emergent Adverse Events Suspected to be Related to Investigational Product by Site                                  | Safety Analysis Set |
| Table 14.3.16.1 | All Ocular Treatment-Emergent Serious Adverse Events in the Study Eye by Site  | Safety Analysis Set |
| Table 14.3.16.2 | All Ocular Treatment-Emergent Serious Adverse Events in the Non-Study Eye by Site  | Safety Analysis Set |
| Table 14.3.16.3 | All Non-Ocular Treatment-Emergent Serious Adverse Events by Site   | Safety Analysis Set |

